#### 4.5.3.2. Vital Signs

Vital signs and change from baseline will be summarized over time. Incidence of treatment-emergent markedly abnormal vital signs during intervention, as defined in [Table 8](#), will be summarized for participants who had a baseline assessment and at least 1 postbaseline assessment for that vital sign. A listing of participants with treatment-emergent markedly abnormal vital signs will be presented. The 4-week window after the last dose or treatment discontinuation will be applied.

**Table 8: Markedly Abnormal Vital Signs**

Vital Sign	Criteria
Pulse	>120 bpm and with >30 bpm increase from baseline
	<50 bpm and with >20 bpm decrease from baseline
Systolic blood pressure	>180 mm Hg and with >40 mm Hg increase from baseline
	<90 mm Hg and with >30 mm Hg decrease from baseline
Diastolic blood pressure	>105 mm Hg and with >30 mm Hg increase from baseline
	<50 mm Hg and with >20 mm Hg decrease from baseline
Respiratory rate	>20 breaths per minute
Temperature	>38°C and with $\geq 1^\circ\text{C}$ increase from baseline

#### 4.5.3.3. Columbia-Suicide Severity Rating Scale

The C-SSRS will be used as a screening tool to prospectively evaluate suicidal ideation and behavior among study participants. The C-SSRS defines 5 subtypes of suicidal ideation and 4 possible suicidal behaviors, as well as non-suicidal self-injurious behavior and completed suicide.

Two versions of the C-SSRS will be used in this study, the *Baseline/Screening* version and the *Since Last Visit* version. The *Baseline/Screening* version will be conducted during the screening visit and the *Since Last Visit* version will be conducted at all other visits.

The following are C-SSRS categories and have binary responses (yes/no). A “yes” response to any C-SSRS category will be assigned a score as below:

##### Suicidal Ideation (1-5)

1=Wish to be Dead

2=Non-specific Active Suicidal Thoughts

3=Active Suicidal Ideation with Any Methods (Not Plan) without Intent to Act

4=Active Suicidal Ideation with Some Intent to Act, without Specific Plan

5=Active Suicidal Ideation with Specific Plan and Intent

##### Suicidal Behavior (6-10)

6=Preparatory Acts or Behavior

7=Aborted Attempt

8=Interrupted Attempt

9=Actual Attempt (non-fatal)

10=Completed Suicide

If no events qualify for a score of 1 to 10, a score of 0 will be assigned (0 = “Negative result [no suicidal ideation or behavior]”). Higher scores indicate greater severity.

Suicidal ideation and behavior will be summarized by C-SSRS categories and intervention group based on the most severe/maximum post baseline C-SSRS outcome or AE of suicidal ideation, suicidal behavior excluding completed suicide, or completed suicide through Week 16, through Week 24, through the reporting period at Week 52 DBL, and through Week 160. The baseline is defined as the most severe/maximum C-SSRS score at either screening or Week 0.

The maximum score assigned for each participant will also be summarized into one of three broad categories: No suicidal ideation or behavior, suicidal ideation, and suicidal behavior. A shift table for change in C-SSRS categories of no suicidal ideation or behavior, suicidal ideation, and suicidal

behavior from baseline through Week 16, through 24, through reporting period of Week 52 DBL, and through Week 160 will be presented, where the baseline category is based on C-SSRS score and the post baseline is based on C-SSRS or AE data.

#### **4.5.3.4. Tanner Staging**

Count and percentage of Tanner scale (range from Stage 1 to Stage 5) will be summarized by gender for adolescent participants with previous Tanner stage <5.

#### **4.5.3.5. PHQ-9**

The PHQ-9 is self-administered, 9-item questionnaire measuring symptoms and severity of depression. The recall period for all items is the past 2 weeks. The items include diminished interest or pleasure, depressed mood, insomnia/hypersomnia, fatigue or loss of energy, weight loss or weight gain/appetite loss or appetite gain, feelings of worthlessness, diminished concentration/indecisiveness, psychomotor agitation/retardation, and thoughts of death/suicide. Each item is rated on a 4-point Likert scale ranging from 0 “not at all” to 3 “nearly every day”. Higher scores indicate more severe depressive symptoms. The PHQ-9 scores for depression range from 0 to 27 with higher scores indicating worse state (more severe depressive symptoms). A score of 5 to 9 is considered to be minimal symptoms of depression. A score of 10 to 14 is considered minor depression, dysthymia, or mild major depression. A score of 15 to 19 is considered to indicate moderately severe major depression, and a score  $\geq 20$  is considered to be severe major depression.

- The shift table will be provided to summarize the shift in values from baseline to postbaseline.
- A listing will be produced for all PHQ-9 score including unscheduled visits for participants with PHQ-9 score  $\geq 15$ .

#### **4.5.3.6. Electrocardiogram**

The Electrocardiogram data will be summarized by ECG parameter. Descriptive statistics will be calculated at baseline and for observed values and change from baseline at each scheduled time point.

In addition, summary of post-baseline ECG abnormalities different from Week 0 and a listing of subjects with any post-baseline ECG abnormalities different from Week 0 measurement will be provided. The 4-week window after the last dose or treatment discontinuation will also be applied.

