Study Procedure																
ss-IGA		X			X		X		X			X		X		W8-W52: collect only for participants with active scalp psoriasis at W0.
sPGA-G		X			X		X		X			X		X		W8-W52: collect only for participants with active genital psoriasis at W0.
hf-PGA		X			X		X		X			X		X		W8-W52: collect only for participants with active palmoplantar psoriasis at W0.
f-PGA		X			X		X		X			X		X		W8-W52: collect only for participants with active nail psoriasis at W0.
mNAPSI		X			X		X		X			X		X		
PGA of Disease Activity		X			X		X							X		Only for participants <18 years of age with a previous diagnosis of PsA at or before screening.
Photography (optional substudy)		X		X			X									
Safety Assessments																
Full physical examination	X	X												X		
Targeted physical examination			X	X	X	X	X	X	X	X	X	X	X			Recommended to include skin and general exam with additional organ systems based on investigator's judgement.
Tanner Staging		X												X		W52: Only for participants <18 years old at screening with previous Tanner stage <5.
Height	X	X					X							X		At screening, W16 and W52: Only for participants <18 years at Screening.
Weight	X	X					X							X		At screening: Only for participants <18 years of age.

Period	Screen-ing	Placebo-controlled					JNJ-77242113 Treatment		Randomized withdrawal and retreatment						Unsch-eduled ^{a,b}	Notes: See Section 1.3.2 for Early Termination Visit procedures.
Week (W)	-5-0	0	2	4	8	12	16	20	24	28	32	36	44	52		
Visit Window (days)			±2	±2	±4	±4	±4	±4	±4	±4	±4	±4	±4	±4		
Study Procedure																
Vital signs	X	X	X	X	X	X	X	X	X	X	X	X	X	X	X	Including temperature, heart rate, respiratory rate, and blood pressure.
12-lead triplicate ECG	X						X							X		
PHQ-9	X	X	X	X	X	X	X	X	X	X	X	X	X	X		
C-SSRS	X	X	X	X	X	X	X	X	X	X	X	X	X	X		
TB evaluation	X	X	X	X	X	X	X	X	X	X	X	X	X	X	X	
Pregnancy test for female participants of childbearing potential	X (serum)	X	X	X	X	X	X	X	X	X	X	X	X	X		A negative urine test result is required at each visit prior to dispensing study intervention. A urine pregnancy test may be performed at any time during the visit including before PROs.
Clinical Laboratory Tests																
Hematology	X	X		X	X	X	X	X	X	X	X	X	X	X		
Chemistry	X	X		X	X	X	X	X	X	X	X	X	X	X		
Lipid panel		X					X							X		Fasting requirement: ≥6 h unless medically contraindicated.
hs-CRP		X					X							X		
Urinalysis		X		X	X	X	X	X	X	X	X	X	X	X		May be performed any time during the study visit including before PRO collection.

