8.3. Safety Assessments

Details regarding the Independent DMC are provided in Committees Structure in [Appendix 2](#), Regulatory, Ethical, and Study Oversight Considerations.

Adverse events will be reported and followed by the investigator as specified in Section 8.4, Adverse Events, Serious Adverse Events, and Other Safety Report and [Appendix 3](#), Adverse Events, Serious Adverse Events, Product Quality Complaints, and Other Safety Reporting: Definitions and Procedures for Recording, Evaluating, Follow-up, and Reporting.

Any clinically relevant changes occurring during the study must be recorded on the Adverse Event section of the CRF.

The study will include the following evaluations of safety and tolerability according to the time points provided in the SoA.

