8.3.2. Electrocardiograms

During the collection of ECGs, participants should be in a quiet setting without distractions (eg, television, cell phones). Participants should rest in a supine position for at least 5 minutes before ECG collection and should refrain from talking or moving arms or legs. If blood sampling or vital sign measurement is scheduled for the same time point as ECG recording, the procedures should be performed in the following order: ECG(s), vital signs, blood draw.

At each time point at which triplicate ECGs are required, 3 individual ECG tracings should be obtained as closely as possible in succession. Details regarding collection of ECGs are available in the site manual.

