In general, all statistical tests will be performed at a significance level of 0.05 (2-sided) unless otherwise specified. Multiplicity adjustment procedure will be used to control the overall Type I error rate for the primary and key secondary endpoints (section 2.1). No adjustments for multiple comparisons will be made for other secondary endpoints and exploratory endpoints. Nominal p-values for other secondary and exploratory endpoints will be reported but should not be used to infer statistical significance.

The baseline measurement for efficacy endpoints is defined as the closest measurement taken prior to or on the first study agent administration date. The baseline measurement for other endpoints

including safety, PK and immunogenicity is defined as the closest measurement taken prior to the time of the first study agent administration.

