#### 4.1.1. Analysis Visit Windows

Unless otherwise specified, nominal visits will be used for all by visit analyses. The study visits scheduled after randomization should occur at the time delineated in the Schedule of Activities of the protocol.

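### SAP 4.5.3.6 compares new ECG abnormalities with a Week 0 ECG that the Schedule of Activities does not include

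*SAP*

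**What the plan says.** SAP Section 4.5.3.6 has two paragraphs. The first plans descriptive statistics by ECG parameter: values at baseline, then observed values and changes from baseline at each scheduled time point. The second adds a "summary of post-baseline ECG abnormalities different from Week 0" and a listing of participants with "any post-baseline ECG abnormalities different from Week 0 measurement".

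For safety data, SAP Section 4.1 sets a general baseline rule: baseline "is defined as the closest measurement taken prior to the time of the first study agent administration".

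The protocol leaves the timing of safety assessments to the schedule: "The study will include the following evaluations of safety and tolerability according to the time points provided in the SoA". In Protocol Section 1.3.1 the row "12-lead triplicate ECG" is marked at Screening, Week 16 and Week 52. Protocol Section 8.3.2 describes how the tracings are taken ("At each time point at which triplicate ECGs are required, 3 individual ECG tracings should be obtained as closely as possible in succession") but names no visit.

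**The concern.** A summary of new abnormalities needs a pre-treatment ECG for comparison. The second paragraph of SAP 4.5.3.6 names Week 0 as that comparator, and the schedule takes no ECG at Week 0. The first paragraph of the same section uses baseline, so the section gives two labels for the reference and only one of them has scheduled data behind it.

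What is at stake is whether these two outputs can separate findings that appear on treatment from findings already present. They are the only ECG outputs in the SAP that classify abnormalities participant by participant. The rest of the section is descriptive statistics, and ECG has no table of outlier thresholds like the one SAP Table 8 gives for vital signs. Protocol Section 9.3.5 describes no ECG analysis that could serve as a fallback.

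**Working it through.** No sample size, power or alpha figure is involved. The check compares the visits at which an ECG is scheduled with the visit that SAP 4.5.3.6 names as reference.

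**Step 1. Read the ECG row of the schedule.** The table was extracted from PDF, so a shifted column had to be ruled out. Three neighbouring rows with the same layout were mapped to the week columns in the same way.

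| Row in Protocol 1.3.1 | Marked visits |
|---|---|
| 12-lead ECG | Screening, 16, 52 |
| Weight | Screening, 0, 16, 52 |
| Full physical examination | Screening, 0, 52 |
| Lipid panel | 0, 16, 52 |

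The neighbouring rows carry Week 0 marks and the ECG row does not. The empty Week 0 cell is therefore not an extraction shift.

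**Step 2. Read the open-label schedule.** In Protocol 1.3.2 the ECG row parses to Week 112, Week 160 and Early Termination. All of these are post-baseline, so none can act as a reference.

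**Step 3. Look for a Week 0 ECG elsewhere.** Protocol 8.3 defers to the schedule, and Protocol 8.3.2 adds no visit. The count is:

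- scheduled ECG visits before the first dose: 1 (Screening);
- scheduled ECGs at Week 0: 0.

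**Step 4. Ask whether a rule turns the screening ECG into a Week 0 ECG.** None was found. SAP 4.1.1 states: "Unless otherwise specified, nominal visits will be used for all by visit analyses". That rule governs by-visit analyses and does not redefine baseline, but it does not relabel a screening record as Week 0 either. SAP 4.5.3.3 treats the two as separate visits: the C-SSRS baseline is the worse of the screening and Week 0 scores.

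**Step 5. Apply the SAP 4.1 rule instead.** The safety baseline is the closest measurement before the first dose. By schedule that is the screening ECG, so every participant who follows the schedule has a reference.

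**Step 6. Sort the outputs in SAP 4.5.3.6.**

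| Output | Reference named | Reference scheduled? |
|---|---|---|
| Descriptive statistics and change by parameter | Baseline | Yes (Screening) |
| Summary of abnormalities | Week 0 | No |
| Listing of participants with abnormalities | Week 0 | No |

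**The case against.** The strongest reply is that Week 0 is simply shorthand for baseline. Protocol 8.2 and a note in the schedule both equate the baseline visit with Week 0. The sentence in question itself speaks of post-baseline abnormalities. SAP 4.1 already defines the safety baseline, the preceding paragraph of 4.5.3.6 uses it, and where the SAP wants a different safety baseline, as for the C-SSRS, it says so. On this view a competent programmer would use the screening ECG without hesitation.

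Most of that stands as evidence of intent: baseline is very likely what was meant. It does not make the written rule correct. The same documents keep Screening and Week 0 apart as visits, and the ECG is one of the assessments for which the difference matters, because it is done at one and not at the other. Using the screening ECG would be sensible, but it would depart from the SAP's words without a stated rule.

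The reply is also right to limit the consequences. A reader might infer that the table will come out empty, or will count every pre-existing abnormality as new. Either could follow from literal programming, but nothing in the documents shows that either would happen. A reader might also infer that ECG safety as a whole cannot separate new from old findings. The documents do not support that: change from baseline is still available, and Protocol 8.3 requires clinically relevant changes to be recorded as adverse events, which are summarised separately.

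**Conclusion.** The text is wrong as written, and its scope is minor. By schedule, the reference named for the ECG abnormality summary and for its listing does not exist. The descriptive and change-from-baseline ECG statistics are unaffected. SAP Section 4.5 plans no formal safety comparison, so no inference depends on these outputs.

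It is tempting to put the size as a missing reference for all of the roughly 600 participants. That only restates that the schedule has no Week 0 ECG; it is not a measured effect. It is also true only by schedule, because an investigator could record an unscheduled ECG on the Week 0 date, although the plan does not call for one.

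The conclusion rests on the column mapping of the extracted schedule, which the neighbouring rows support, and on there being no other instruction for a Week 0 ECG in the protocol or SAP.

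**What to change.** In the second paragraph of SAP 4.5.3.6, replace Week 0 with: baseline (closest ECG before the first dose, per SAP Section 4.1). Make the change in both the summary and the listing.

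Do not write the screening visit into the definition. If a pre-dose ECG were repeated or taken unscheduled after screening, a fixed reference to screening would conflict with the closest-measurement rule in SAP 4.1.

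The cost is one term changed in two places. It needs no new data, no added ECG, no protocol amendment and no change to any other analysis.

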### **4.6. Other Analyses**

#### **4.6.1. Pharmacokinetics**

##### **4.6.1.1. JNJ-77242113 Concentrations**

PK analyses will be performed on the PK analysis set, defined as participants who have received at least 1 dose of JNJ-77242113 and have at least 1 valid blood sample drawn for PK analysis after their first dose of JNJ-77242113.

Descriptive statistics (N, mean, SD, median, range, coefficient of variation [%CV], and interquartile [IQ] range) will be used to summarize JNJ-77242113 concentrations at post-dose sampling time intervals classified as peak, intermediate and trough. PK data may be displayed graphically, such as mean  $\pm$  SD PK concentrations over time by intervention group.

The following analyses will be performed as appropriate.

- Summary of plasma JNJ-77242113 concentration over time
- Proportion of participants with plasma JNJ-77242113 concentration below the lowest quantifiable concentration in a sample at each visit
- Plots of median plasma JNJ-77242113 concentrations over time

JNJ-77242113 concentrations below the lowest quantifiable concentration will be imputed as zero in the summary statistics. All plasma concentrations below the lowest quantifiable concentration or missing data will be labeled as such in the concentration database.

All participants and samples excluded from the analysis will be clearly documented.

If sufficient data are available, then population PK analysis using plasma concentration-time- data of JNJ-77242113 will be performed using nonlinear mixed-effects modeling. Data may be combined with those of other selected studies to support a relevant structural model. Available baseline participant characteristics (e.g., demographics, laboratory variables, race) will be evaluated as potential covariates affecting PK parameters. Details will be given in a population PK analysis plan and the results of the analysis will be presented in a separate report.

#### **4.6.1.2. Data Handling Rules**

Unless otherwise specified, the following data handling rules will apply to PK sample analyses:

- Plasma concentration summaries will be based on the actual treatment received.
- All plasma concentration summaries for a particular timepoint will include data obtained from treated participants at the timepoint of interest without imputing any missing data.
- A concentration not quantifiable (below the lower limit of quantification) will be treated as 0 in the summary statistics and shown as the lower limit of quantification ( $<$  LLOQ) in the data listings.
- The data from a participant who discontinued study agent will be excluded from the by-visit data analyses from that point onwards. In addition, the data from a participant who received an incomplete/ incorrect or skipped dose based on the dose prior to the PK sample collection will be excluded for that visit.

#### **4.6.2. Immunogenicity**

##### **4.6.2.1. Antibodies to JNJ-77242113**

The incidence and titers of antibodies to JNJ-77242113 will be summarized for all participants who receive at least 1 dose of JNJ-77242113 and have appropriate samples for detection of

antibodies to JNJ-77242113 (i.e., participants with at least 1 sample obtained after their first dose of JNJ-77242113).

Sample ADA status and sample titer as well as the cumulative participant ADA status and peak titer through the visit will be coded and provided by the bioanalytical group.

Participants with treatment-emergent antibodies to JNJ-77242113 include participants with treatment-induced antibodies to JNJ-77242113 and treatment-boosted antibodies to JNJ-77242113.

Participants with treatment-induced antibodies to JNJ-77242113 will have a sample that is negative for antibodies to JNJ-77242113 prior to JNJ-77242113 administration and at least one sample that is positive for antibodies to JNJ-77242113 after JNJ-77242113 administration.

Participants with treatment-boosted antibodies to JNJ-77242113 will have a sample that is positive for antibodies to JNJ-77242113 prior to JNJ-77242113 administration and at least one sample that is positive for antibodies to JNJ-77242113 after JNJ-77242113 with a 4-fold increase in titer over baseline.

If the titer remains the same or increases less than 4-fold after intervention or if ADA titer reduces or ADA disappears, the participant is classified as “treatment-emergent ADA negative”. Participants with baseline negative and all post intervention samples negative are also classified as “treatment-emergent ADA negative”. Participants that are unavailable for treatment-emergent ADA following intervention will be classified as “participants with baseline samples only”, i.e., no appropriate sample is available after intervention.

The antibodies to JNJ-77242113 summary and analysis will be based on the observed data; therefore no imputation of missing data will be performed. Note: participant status is through each visit, thus, participant status and peak titers may change as the study progresses over time. Therefore, the ‘participant ADA status’ at a visit represents the cumulative ADA status through that visit. For example, datasets through Week 24 will have participant level status (e.g., negative) but at Week 52, they may have developed ADA and the participant status becomes “treatment-emergent ADA positive” from the interim to the final DBL. Peak titers can also change (increase) if a higher titer occurs after an initial DBL.

Incidence of antibody (evaluable, treatment-emergent ADA positive, treatment-emergent ADA negative) status will be summarized.

In addition, listings of participants with baseline positive ADA samples, participants who are classified as positive for treatment-emergent antibodies to JNJ-77242113 and participants who discontinue the study agent by antibodies to JNJ-77242113 status may be presented. The sample antibody status, and the titer will be listed by visit. This listing will also provide information regarding JNJ-77242113 plasma concentration and select efficacy parameters.

#### 4.6.2.2. Other Immunogenicity Analyses

The following analyses may be conducted if there is a sufficient number (eg,  $\geq 20$ ) of participants that are ADA positive.

**Treatment-induced Onset** (data summarized will be exclusive to baseline negative participants)

Descriptive statistics for days from first administration of study intervention to the date of first instance of treatment-induced ADA (positive for treatment-induced antibody) will be summarized.

Number of days until first instance of treatment-induced ADA = (First date for positive antibody - Date of first administration of study intervention + 1);

**Duration of Treatment-induced ADA** (data summarized is exclusive to baseline negative participants).

The duration of treatment-induced ADA refers to the longevity of treatment-induced ADA.

Descriptive statistics for duration of treatment-induced ADA among those who developed antibody will be summarized.

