2. INTRODUCTION

IL-23 is a disulfide-linked heterodimer of the IL-23p19 and IL-12/23p40 subunits. The receptor for IL-23 comprises the IL-23R and IL-12R subunits (Bloch 2018). IL-23p19 binding to the N-terminal immunoglobulin-like domain of IL-23R is followed by IL-12/23p40 binding to IL-12R β 1. Ligand binding leads to phosphorylation and nuclear translocation of STAT proteins.

JNJ-77242113 is a peptide that binds directly to the IL-23R subunit and prevents IL-23 binding, thereby inhibiting proximal IL-23R signaling and downstream effector functions (eg, cytokine secretion). JNJ-77242113 has high potency with an IC₅₀ of ~20-30 pM in peripheral human cell based functional assays. Despite its low oral bioavailability (<1%), JNJ-77242113 has demonstrated systemic effects and has provided substantial efficacy in plaque psoriasis clearance in doses 25 mg once daily and greater in the Phase 2b Study, 77242113PSO2001. Therefore, JNJ-77242113 is a promising candidate for further development in systemic, IL-23-driven diseases, such as plaque psoriasis.

To date, JNJ-77242113 has been studied in several Phase 1 and Phase 2 studies. For the most comprehensive nonclinical and additional clinical information regarding JNJ-77242113, refer to the latest version of the IB and Addenda for JNJ-77242113.

The term “study intervention” throughout the protocol, refers to study agent as defined in Section 6.1. Study Intervention(s) Administered.

The term “sponsor” used throughout this document refers to the entities listed in the Contact Information page(s), which will be provided as a separate document.

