6. STUDY INTERVENTION AND CONCOMITANT THERAPY

6.1. Study Intervention(s) Administered

The study intervention will be provided as tablets for oral administration.

For adult participants:

For adult participants, the study intervention must be swallowed whole. Participants will be instructed to take the study intervention at approximately the same time every day upon waking with 240 mL (8 oz) water on an empty stomach (no food intake for at least 2 hours before and for at least 30 minutes after taking the study intervention).

For adolescent participants:

For adolescent participants, the participant's legal guardian or caregiver may assist with administration of the study intervention.

For adolescent participants, the study intervention should be swallowed whole. Adolescent participants will be instructed to take the study intervention at approximately the same time every day upon waking with 240 mL (8 oz) water on an empty stomach (no food intake for at least 2 hours before and for at least 30 minutes after taking the study intervention).

If adolescent participants have difficulty swallowing tablets, the study intervention may be suspended in a glass of water and taken within 15 minutes. It may take a few minutes for the tablet to fully disperse. The tablet may not disperse completely (milky to cloudy appearance), and small pieces may be seen in the water and are safe to swallow. After drinking the study intervention, rinse and swirl the glass with more water and swallow to ensure all the study intervention is taken. The total amount of water to be used for the dispersion of the tablet and rinsing should be at least 240 mL (about 8 oz or 1 cup).

Study personnel should review dose administration requirements with the participant, as appropriate, and with the delegated caregiver(s) before administration and throughout the study as necessary.

Designation	Product			
Investigational Medicinal Product(s)	JNJ-77242113, placebo for JNJ-77242113			
	Authorization status in the EU/EEA			
	
 
 Authorized	Not applicable	
 
 Unauthorized	JNJ-77242113, placebo for JNJ-77242113	
 
	Authorized	Not applicable	Unauthorized
Authorized	Not applicable			
Unauthorized	JNJ-77242113, placebo for JNJ-77242113			
NIMP/AxMP	Not applicable			

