    - Week 16 to Week 156: Participants will cross-over to receive JNJ-77242113 200 mg once daily through Week 156.
- Adolescent participants
  - JNJ-77242113 200 mg once daily
    - Week 0 to Week 156: Participants will be treated with JNJ-77242113 200 mg once daily
    - Adolescents will not participate in re-randomization regardless of their PASI score at Week 24.
  - Placebo to JNJ-77242113 200 mg once daily
    - Week 0 to Week 16: Participants will receive placebo once daily through Week 16.
    - Week 16 to Week 156: Participants will cross-over to receive JNJ-77242113 200 mg once daily through Week 156.

[figure not shown]
This study includes a 5-week screening period, a placebo-controlled period through Week 16 and a randomized withdrawal and retreatment period from Week 24 through Week 52. At Week 52, participants will be transitioned to open-label JNJ-77242113 through Week 156. All

participants will have a 4-week safety follow-up period after the last administration of study intervention or at the end of the treatment period. The total duration of this study for each participant is approximately 165 weeks.

The first database locks (DBL) will occur when all participants (adults and adolescents) complete Week 24 of the study. An additional DBL will occur after all adult participants complete Week 52 of the study. Additional DBLs may occur between Week 52 and Week 160 to support publication or regulatory submissions. The final DBL will occur when all participants complete the study.

An independent DMC will be commissioned for this study to review the safety data on an ongoing basis. A diagram of the study design is provided [Figure 1](#).

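### The ADA onset formula starts at the first study-intervention dose, which is placebo for crossover participants, so an onset after crossover is overstated by about 112 days; the ADA baseline has a related ambiguity

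*SAP*

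**What the plan says.** SAP 4.6.2.2 describes time to first treatment-induced ADA as "First date for positive antibody - Date of first administration of study intervention + 1". The summary is restricted: "data summarized will be exclusive to baseline negative participants". It is also conditional: "The following analyses may be conducted if there is a sufficient number (eg", with 20 or more ADA-positive participants given as the example.

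Protocol Section 2 explains that the term study intervention "throughout the protocol, refers to study agent as defined in Section 6.1". Section 6.1 lists the investigational products as "JNJ-77242113, placebo for JNJ-77242113". For the placebo arm, SAP 1.2 says of the time from Week 16: "Participants will cross-over to receive JNJ-77242113 200 mg once daily through Week 156".

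Two other rules bear on ADA status:
- SAP 4.1 sets the baseline for endpoints "including safety, PK and immunogenicity is defined as the closest measurement taken prior to the time of the first study agent administration".
- SAP 4.6.2.1 says that a participant with treatment-induced antibodies "will have a sample that is negative for antibodies to JNJ-77242113 prior to JNJ-77242113 administration" and at least one positive sample afterwards. The treatment-boosted class needs a positive sample before JNJ-77242113, and a later positive with a 4-fold titer increase over baseline.

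**The concern.** Time to ADA is meant to describe how soon antibodies appear after exposure to the peptide. For a crossover participant the formula's clock starts on the first placebo tablet, 16 weeks before any exposure. The resulting values describe the trial calendar rather than the drug.

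The SAP uses the drug-specific anchor elsewhere. The Immunogenicity Analysis Set (SAP Section 3) and the induced and boosted definitions (4.6.2.1) refer to JNJ-77242113. The Week 52 safety summary for the crossover group (4.5) counts only events from Week 16 onward. The onset formula departs from that logic.

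The baseline rule raises a separate question: whether an antibody, or a titer rise, that first appears on placebo can be credited to the drug. This matters more widely than the onset summary, because the ADA classes feed the planned summary of treatment-emergent ADA status (4.6.2.1) and the possible summaries of efficacy, PK and safety by ADA status (4.6.2.4).

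**Working it through.** **Inputs**
- Allocation: 600 participants, 2:1 (SAP Section 5).
- Placebo period: Week 0 to Week 16, which is 16 × 7 = 112 days (SAP 1.2).
- Week 16 visit window: ±4 days (Protocol 1.3.1).
- Scheduled ADA samples to Week 52: Weeks 0, 4, 12, 16, 28, 36 and 52 (Protocol 1.3.1).

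**The plan's own figure.** The documents state no onset time. The allocation reproduces: 600 × 2/3 = 400 active and 600 × 1/3 = 200 placebo.

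**Onset for a crossover participant whose first positive is at week w, after crossover**
- As written: 7w + 1.
- From the first JNJ-77242113 dose: 7w − 112 + 1.

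| First positive | As written | From first JNJ-77242113 dose | Ratio |
|---|---|---|---|
| Week 28 | day 197 | day 85 | 2.3 |
| Week 36 | day 253 | day 141 | 1.8 |
| Week 52 | day 365 | day 253 | 1.4 |

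The difference is 112 days in each row. If the Week 16 visit falls 4 days early or late it is 108 or 116 days, and the Week 28 value from first drug is day 89 or day 81. Participants randomized to JNJ-77242113 are unaffected.

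**First positive on placebo.** The formula does not require the positive sample to follow the drug. A first positive at Week 4 gives day 29 (4 × 7 + 1), although it precedes the first JNJ-77242113 dose by 112 − 28 = 84 days. At Week 12 it gives day 85, which is 112 − 84 = 28 days before that dose.

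**Effect on a pooled mean.** SAP 4.6.2.2 does not say whether arms are pooled. If they are, the mean shifts by 112 × (crossover share of onset times):
- Share 200/600: 112 × 1/3 ≈ 37 days. This assumes equal ADA incidence in both arms and that all placebo participants cross over.
- Share 20% (assumed): about 22 days.
- Share 10% (assumed): about 11 days.

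If onset is shown by arm, the crossover arm shifts by the full 112 days, again for first positives after crossover.

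**Classification: two patterns in a crossover participant**
- *Negative at Week 0, positive at Week 12 on placebo, positive at Week 28.* Week 0 is a negative sample before JNJ-77242113 and Week 28 is a positive one after it, so the induced wording is met. Under SAP 4.1 the participant is also baseline negative. But Week 12 is a positive sample before JNJ-77242113, so the participant equally fits the pre-drug-positive wording, which leads to the boosted rule or to treatment-emergent negative. The text does not say which pre-drug sample decides.
- *Titer T at Week 0, 4T at Week 12 and Week 16 on placebo, 4T at Week 28.* Against the Week 0 baseline the ratio is 4 and the boosted rule is met. Against the last pre-drug sample the ratio is 1 and it is not.

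**The case against.** The strongest reply is about importance. The onset summary may never be produced, it is descriptive, and immunogenicity is an exploratory objective whose listed endpoint is ADA incidence, which does not use this formula. No hypothesis test depends on it. Scheduled samples after Week 16 are 8 to 16 weeks apart, so onset is known only coarsely. No ADA sample is scheduled between Week 16 and Week 28, so crossover participants should add almost nothing at the Week 24 database lock. All of this stands and limits the weight of the point. It does not make the formula right.

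A reader might infer that the onset formula itself causes a pre-existing antibody to be labelled treatment-induced. The documents do not support that. The formula assigns no label; SAP 4.6.2.1 does, and it refers to JNJ-77242113 administration. An antibody already present at Week 0 is not baseline negative and stays out of the onset summary. What remains is narrower: antibodies or titer rises that first appear between Week 0 and Week 16 on placebo, and the source is the pairing of SAP 4.1 with 4.6.2.1.

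Even there, the induced reading is one of two. SAP 4.6.2.1 also leaves the coding of ADA status to the bioanalytical group, which may apply a sensible convention, although the SAP does not state one. The pattern requires placebo recipients to test positive for antibodies to a drug they have not taken, and the available text gives no rate for that.

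A reader might also take one third as the share of onset times affected, or 37 days as a firm bias. One third is the randomized share. The share in the onset summary is unknown, and placebo participants who never cross over are excluded from the Immunogenicity Analysis Set.

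**Conclusion.** The point holds for the onset formula. As written, it adds about 112 days (108 to 116) to onset for every crossover participant whose first positive sample follows the Week 16 switch. At Week 28 that turns day 85 into day 197. This rests only on the stated formula, the protocol's definition of study intervention, and the visit schedule. The 37-day pooled shift is conditional on pooling, equal incidence and complete crossover.

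The classification issue is separate and less certain. For the boosted class, a Week 0 baseline lets a rise on placebo meet the 4-fold rule. For the induced class, the wording supports two answers.

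This is a wrong anchor in an optional exploratory summary, plus an under-specified ADA baseline. It is worth correcting because it concerns a designed feature of the trial, the crossover of about 200 participants, and costs little. The efficacy conclusions are not affected.

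**What to change.** 1. In SAP 4.6.2.2, count days from the date of the first JNJ-77242113 administration, and use only positive samples after that dose.
2. In SAP 4.6.2.1, define the ADA baseline as the last available sample before the first JNJ-77242113 dose. For participants randomized to JNJ-77242113 this is Week 0. For crossover participants it is the Week 16 sample if drawn before dosing, otherwise the latest earlier sample. Use this baseline for both the negative-baseline and the 4-fold rules.
3. Confirm that the bioanalytical coding of ADA status follows the same definition.

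The cost is a few lines of SAP text, one anchor date in programming, and a check of Week 16 timing. That check is needed because Protocol 1.3.1 requires blood before dosing only at Week 0. At Week 16 it specifies pre- and post-dose draws for PK, and lists an ADA sample without timing relative to the dose. No new samples are required.
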